### 9.3 Vital Sign Measurements

Vital signs will include systolic and diastolic blood pressure, pulse rate, respiratory rate, and body temperature, and will be measured at the time points indicated in the schedule of assessments (refer to Section 3 of the protocol).

The number and proportion of normal and abnormal treatment-emergent vital signs will be summarized. Abnormalities are defined as:

Variable	Unit	Low	High
SBP	mmHg	$\leq 90$ mmHg AND change from baseline $\leq -20$ mmHg	$\geq 180$ mmHg AND change from baseline $\geq 20$ mmHg
DBP	mmHg	$\leq 50$ mmHg AND change from $\leq -15$ mmHg	$\geq 105$ mmHg AND change from baseline $\geq 15$ mmHg
Pulse rate	bpm	$\leq 50$ bpm AND change from baseline $\leq -15$ bpm	$\geq 120$ bpm AND change from baseline $\geq 15$ bpm

Variable	Unit	Low	High
Body temperature	C	Not applicable	$\geq 38.3\text{ }^{\circ}\text{C}$ AND change from baseline $\geq 1.1\text{ }^{\circ}\text{C}$
Weight	kg	Percent change from baseline $\leq -7.0\text{ \%}$	Percent change from baseline $\geq 7.0\text{ \%}$

All vital sign, body weight, and height measurements will be presented in a data listing. Where indicated, abnormalities will appear in the listing.

#### 9.4 Physical Examination

All physical examination results will be presented in a data listing.

#### 9.5 Electrocardiograms

Triplet 12-lead ECG recordings will be performed at screening, on Day 6 and Day 28 after the subject has been in the supine position for at least 5 minutes. Mean of the triplicated measurements of the following will be reported: RR interval, PR interval, QRS width, QT interval, and Fridericia's corrected QT interval (QTcF). The investigator will perform an overall evaluation of the ECG and the recording will be reported as "normal", "abnormal clinically significant" or "abnormal not clinically significant". All ECG data will be summarized in a shift table and presented in a data listing.

### 10. Missing data handling

In general, observed data will be used in statistical analysis without imputation, unless missing data will jeopardize the integrity of the study or pose a problem in the validity of the analysis. A data-as-observed (DAO) approach will be used to evaluate the primary endpoint. Uncertain viral load measurements that are below the lower limit of quantification (LLOQ) will be set to  $0.5 \times \text{LLOQ}$  in the viral load summaries and indicated as BLQ in the listings. If subjects withdraw early, the outcome measure up to point of study withdrawal will be used.

Impact of missing data will be assessed, and ad-hoc sensitivity analysis will be performed when deemed appropriate. No imputation is planned for the primary efficacy analysis, as the study allows replacement when a subject withdraws without any post-baseline virology data and a mixed model will be used. If at a particular time point, the amount of missing data in the AT-752 arm is greater than 10% due to dropout, the impact will be assessed. In this case, an ad-hoc sensitivity analysis using multiple imputations will be performed using the Markov chain Monte Carlo (MCMC) method to impute non-monotone missing data, and a copy reference (i.e. placebo) approach to impute monotonic missing data in the AT-752 arm.

For safety data, missing and partial dates will be programmatically handled according to the following standards: if the day of the month is missing for any date used in a calculation, the 1st of

the month will be used to replace the missing date unless the calculation results in a negative time duration (e.g., date of resolution cannot be prior to date of onset; if replacing resolution date with the 1st of the month results in a negative duration, the resolution date will be set to the onset date). In this case, the date resulting in 0 time duration will be used. These standards are also used if both month and day are missing (Jan 1 unless negative time duration, durations will be reset to 1 day).

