# **7. Treatments and Medications**

## **7.1 Prior and Concomitant Medications**

Medications that stop prior to the first dose of study drug will be classified as prior medication. Medications that start on or after the first dose of study drug will be classified as concomitant. If a

medication starts before the first dose of study drug and stops on or after the first dose of study drug, then the medication will be classified as both prior and concomitant.

All prior and concomitant medications will be coded according to the World Health Organization Drug Dictionary (version to be delineated in the CSR) and presented in a data listing.

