### 9.1 Adverse Events

An AE is defined as any untoward medical occurrence associated with the use of a drug in humans, whether or not considered drug related. The AE's relationship to study treatment will be evaluated by the investigator. The following relationships will be collected on eCRF: not related, or related. If the relationship information is missing, the AE will be considered related in the summary but will be presented as missing in the data listings.

A treatment-emergent AE (TEAE) is defined as any event not present before exposure to study drug or any event already present that worsens in intensity or frequency after exposure. The time frame for treatment emergent adverse events in this study is from the first dose through Day 28 or withdrawal from the study, whichever happens first. TEAE that are evaluated as possibly related to study drug, regardless of timing, will be considered treatment-related TEAE for summary purpose.

The severity of AEs will be classified by the investigator as Grade 1 mild, Grade 2 moderate, Grade 3 severe, Grade 4 potentially life threatening and Grade 5 death. If the severity information is missing, the AE will be considered severe in the summary but will be presented as missing in the data listings.

In all AE summaries, a subject with 2 or more events within the same level of summarization will be counted only once in that level using the most severe incident or most related incident. Percentages will be based on the number of subjects in the safety population.

An overall AE summary will be generated presenting the frequency and percentage of subjects for the following:

- Any TEAE
- Any treatment related TEAE
- Any TEAE of grade 2 or higher
- Any treatment related TEAE of grade 2 or higher
- Any TEAE of grade 3 or higher
- Any treatment related TEAE of grade 3 or higher
- Any SAE
- Any treatment related SAE
- Any treatment related AE leading to early study drug discontinuation
- Any treatment related AE leading to early study discontinuation
- Any death

All AEs will be coded using MedDRA (version 24.1 or up). The TEAEs will also be summarized by system organ class (SOC), preferred term (PT), by severity and relationship to treatment. These TEAE summary tables will be sorted by SOC and PT. System organ class will be displayed in descending order of overall frequency then alphabetically. Preferred term will be displayed in descending order of overall frequency and then alphabetically within SOC.

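### SAP 10 sets a partial AE onset date to the 1st of the month without clearly protecting it against the first dose date, so a new post-dose event can fall outside the TEAE window

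*SAP*

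**What the plan says.** SAP 10 (Missing data handling) gives one convention for partial safety dates. It applies "if the day of the month is missing for any date used in a calculation", with no separate treatment of AE onset. The 1st of "the month will be used to replace the missing date unless the calculation results in a negative time duration". The only illustration of that exception is that the "date of resolution cannot be prior to date of onset"; when the exception applies, "the date resulting in 0 time duration will be used". If day and month are both missing, the replacement is "Jan 1 unless negative time duration".

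SAP 9.1 (Adverse Events) defines a TEAE as "any event not present before exposure to study drug or any event already present that worsens in intensity or frequency after exposure". It adds: "The time frame for treatment emergent adverse events in this study is from the first dose through Day 28", or withdrawal if sooner. It has worst-case rules for two other missing items: missing relationship counts as related, and missing severity counts as severe. It has no rule for a missing onset date.

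SAP 4 assigns negative study days to dates before first dose. SAP 7.1 states: "Medications that stop prior to the first dose of study drug will be classified as prior medication".

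**The concern.** The 1st of the month is the earliest date that a missing day allows. Used for an onset date, it pushes the event towards, and usually past, the start of treatment. The illustrated exception does not stop this: moving an onset earlier lengthens the time to resolution, so that duration cannot turn negative.

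The imputed date is also implausible in this trial. First dose is to be given no later than 24 hours after screening (SAP 3.1). AEs are collected from screening (SAP Schedule of Events), and a stable condition present at screening is not reported as an AE (Protocol 7.3.1.3). A new AE whose recorded month is the dosing month therefore almost certainly began after dosing or within the day before it. The rule gives it a date that will often precede screening.

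At stake is the incidence and grade of TEAEs, a secondary endpoint (SAP 3.2.2), in groups of 15. The direction also runs against the SAP's own worst-case handling of missing severity and relationship.

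**Working it through.** The plan states no figure on this point, so there is none to reproduce. The check applies the rule to the calendar.

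**Inputs.** Imputed onset is the 1st of the onset month, or 1 January (SAP 10). Study Day is date − first dose date + 1 on or after first dose, otherwise date − first dose date (SAP 4). The TEAE window opens at first dose (SAP 9.1). There are 15 subjects per active arm and 3 × 5 = 15 pooled placebo subjects (SAP 3.1 and 4). Assumptions: a 365-day year, with first-dose dates and true onset days spread uniformly.

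**Example.** First dose 15 September, true onset 18 September, day missing.
- True Study Day: 18 − 15 + 1 = 4, inside the window.
- Imputed onset 1 September: Study Day 1 − 15 = −14, outside it.

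**Dose dates exposed.** The imputed onset precedes first dose unless dosing was on the 1st: (365 − 12)/365 = 353/365 = 96.7%. This is a share of dose dates, not of AEs.

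**Share of truly post-dose AEs moved, day missing.** An event is moved if its onset is in the dosing month and dosing was not on the 1st. Onset in a later month is safe, because the 1st of that month follows first dose.

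| | True onset Days 1–5 | True onset Days 1–28 |
|---|---|---|
| All dose-date and onset-day pairs | 365 × 5 = 1,825 | 365 × 28 = 10,220 |
| Onset in dosing month | 1,825 − 12 × (0+1+2+3+4) = 1,705 (93.4%) | 10,220 − 12 × (0+1+…+27) = 5,684 (55.6%) |
| Of these, dosed on the 1st | 12 × 5 = 60 | 12 × 28 = 336 |
| Moved before first dose | 1,645 | 5,348 |
| As share of dosing-month onsets | 96.5% | 94.1% |
| As share of all onsets | 90.1% | 52.3% |

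**Day and month missing.** The event escapes only if dosing was on 1 January or onset fell in the next calendar year.
- Days 1–5: 1 − (5 + 10)/1,825 = 99.2% moved.
- Days 1–28: 1 − (28 + 378)/10,220 = 96.0% moved.

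**Effect on a table.** One subject in 15 is 1/15 = 6.7 percentage points. SAP 9.1 counts a subject once per level of summarization, so this is a ceiling per affected subject, reached only if no other event keeps that subject in the row.

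**Medications.** Take a medication started before dosing whose stop day is missing in the dosing month. The stop date becomes the 1st, or the start date if the 1st would give a negative duration. Unless dosing was on the 1st, both precede first dose, so the medication is classed as prior only even if it was taken on treatment.

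**The case against.** The best defence is that the negative-duration exception is worded generally and resolution before onset is only an example. Onset minus first dose can also be negative, and resetting it to zero would put the onset on the dose date. This reading is possible, so it cannot be said flatly that the exception never protects an onset date. It is not the natural reading: treatment emergence is a comparison of dates rather than a duration, and SAP 4 accepts negative study days. Two programmers could produce different TEAE tables from this text, which is itself a reason to amend it.

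Other limits stand in full:
- Events that worsen after exposure remain TEAEs. The SAE and death rows are not restricted to TEAEs, and all AEs are listed. SAP 9.1 also has a sentence counting possibly related TEAEs whatever their timing, which may keep related events, although it starts from events that are already TEAEs.
- Partial onset dates should be rare. AEs are assessed at visits on Days 1–8, 14 and 28, onset time is a collected field (Protocol 7.3.1.3), and the eCRF flags discrepancies (Protocol 10.2.2.8). Recall matters mainly between Days 8 and 28.
- SAP 4 declares the analyses descriptive.

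A reader might infer that the rule favours AT-752. The documents do not support that: it applies equally to placebo, so what follows is a possible understatement of incidence in every arm, not a shown distortion of the comparison. Nor do they support a claim that AE durations or concomitant medications are misreported in tables. No AE-duration summary is planned, an onset moved earlier lengthens a duration, and SAP 7.1 only lists medications. The 0-day and 1-day reset values are loose wording: under the inclusive counting in SAP 4 and 7.3, a zero date difference is one day.

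**Conclusion.** The point holds as a defect in a stated rule, limited to new AEs with a missing onset day in the dosing month (or with day and month both missing). On the default reading of SAP 10, such an event is dated before treatment for 96.7% of dose dates. It then leaves the TEAE tables unless it worsened after exposure or is kept by the sentence on related events. TEAE incidence can be understated in any arm, by at most 6.7 percentage points per affected subject in a group of 15. The calendar shares assume uniform dose and onset dates. How many events are affected depends on the number of partial onset dates, which the documents do not give and which is probably small. The case for acting rests on the near-certain misclassification of each such event, the conflict with the SAP's other worst-case rules, and the low cost of repair, not on a large expected effect.

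**What to change.** In SAP 10, with a cross-reference in SAP 9.1, give AE onset its own rule:

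- If the known parts of a partial onset date are compatible with onset on or after first dose, set onset to the first dose date or, where the known month is later than the dosing month, to the 1st of that month. Count the event as treatment-emergent.
- Exception: a recorded stop date shows that the event ended before first dose. Judge this on the recorded parts of the stop date, not on an imputed one.

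Under this rule, no truly post-dose AE with a missing onset day is moved before first dose, against 96.5% (Days 1–5) or 94.1% (Days 1–28) of dosing-month onsets now.

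Two secondary edits affect listings only. Do not class a medication as prior only when its partial stop date is compatible with use on or after first dose. State one reset value for durations in place of 0 days and 1 day.

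The cost is a few lines of text and routine programming, settled before unblinding, with no change to design or data collection. The trade-off is that an AE arising between screening and first dose, an interval of at most 24 hours, may occasionally be counted as treatment-emergent.

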## 11. Pharmacokinetics

Plasma PK concentrations for CCI, AT-551, AT-229, AT-219 and AT-273 will be summarized for each nominal scheduled collection time. Summaries will include descriptive statistics (number of subjects, arithmetic mean, SD, coefficient of variation (CV), geometric mean, geometric CV, median, minimum, and maximum) and the number/percentage of samples reported as below the limit of quantification (BLQ).

All PK listings and individual concentration-time profiles will be presented for the AT-752 treated safety population. Plasma concentration versus actual time profiles for each subject will be presented graphically by treatment using a semi-logarithmic scale. The mean plasma concentration versus scheduled time profiles will be presented graphically by treatment using a semi-logarithmic scale.

### 11.1 Data handling

Data rounding specifications for PK data are documented in the PK table list figure (TLF) shells.

Plasma concentrations that are BLQ will be treated as zero for calculation of concentration descriptive statistics; if <3 values are above the lower limit of quantification (LLOQ) at one time point, the arithmetic mean, SD, and CV will not be reported at that time point. For PK parameter analysis, all BLQ values will be treated as zero, with the exception of BLQ values observed between 2 quantifiable concentrations which will be set to missing. For the estimation of geometric mean and geometric CVs, all BLQ values will be set to missing.

### 11.2 Plasma Pharmacokinetic Parameters

Plasma parameters derived from plasma samples using non-compartmental analysis with Phoenix® WinNonlin® Version 8.3 or higher (Certara USA, Inc., Princeton, NJ) or SAS Version 9.4 or higher (SAS Institute Inc., Cary, North Carolina), as appropriate.

PK samples will be obtained on Day 1 (predose) and at 24 hours after Dose 1(before Dose 4 for TID dosing and before Dose 3 for BID dosing). For TID dosing, intensive PK samples will be obtained before Dose 7 and 0.5, 1, 2, 4, and 6 hours after Dose 7. This serial PK sampling may be done for Dose 7, 8, or 9, based on site/patient convenience. For BID dosing, intensive PK samples will be

obtained before Dose 5 and 0.5, 1, 2, 4, 6, and 8 hours after Dose 5. This serial PK sampling may be done for Dose 5, 6, 7, based on site/patient convenience. For blood samples (both TID and BID dosing), there is a  $\pm 10$ -minute window for time points  $\leq 4$  hour and a  $\pm 15$  minute window for the time points between 4 and 24 hours.

Noncompartmental analysis will be used to estimate the following PK parameters, when applicable and if data permit: **CCI** [REDACTED], AT-551, AT-229, AT-219 and AT273:

$C_{trough}$	Observed trough (predose) concentration (TID on Dose 7, BID on Dose 5). AT-273
$C_{max}$	Maximum observed concentration.
$T_{max}$	Time of maximum observed concentration.
$AUC_{last}$	AUC from time 0 to the last measurable observed concentration ( $C_t$ ), calculated using the linear trapezoidal rule.
$AUC_{tau}$	AUC within a dosing interval, calculated using the linear trapezoidal rule.

For each PK parameter, only subjects with sufficient concentration data to support accurate estimation of at the PK parameter will be included the summary.

Actual sampling times will be used for the estimation of all plasma PK parameters, and all concentrations will be included in the analysis (including concentrations collected outside predefined collection windows). Predose concentrations collected prior to subsequent doses will be included in the PK parameter calculation for the previous dose, where appropriate.

PK parameters of **CCI** [REDACTED], AT-551, AT-229, AT-219 and AT-273 (plasma) will be summarized by treatment and ethnicity using descriptive statistics (number of observations, arithmetic mean, SD, CV, geometric mean, geometric CV, median, minimum, and maximum).  $T_{max}$  will be summarized using number of observations, median, minimum, and maximum values.

## 12. Pharmacodynamics

Change from baseline in DENV viral load (as measured by viral titer) from baseline will be analyzed with repeated measures mixed model using the method of restricted maximum likelihood (REML). The model will include baseline viral load, treatment, time, and treatment-by-time interaction as fixed factors. An unstructured covariance matrix will be specified for the repeated statement. In case a mixed model with unstructured (UN) covariance matrix fails to converge, a compound symmetry (CS) structure will be used as an alternative. If neither of these converges, independent (ID) structure will be used. The treatment group least squares mean (LSM) estimates for mean change from baseline and treatment group differences at each time point, with 80% CI, 95% CI and p-value will

be presented. If none of the covariance structures converge, only descriptive summaries will be included.

Area under the change of the log 10-transformed viral load curve (AUC) from first dose to the end of treatment (Day 5-6) and to study end (Day 28) will be presented by treatment.

AUCD5 and AUCD28 refer to area under the log 10-transformed viral load curve (AUC) from first dose to the end of treatment (Day 5) and to study end (Day 28) respectively. The following rules will be followed for the area under the curve derivation.

- A time-scaled trapezoidal rule will be used for AUC calculation.
- AUC will be calculated from the log 10-transformed viral load curve connecting baseline or the first available viral load measurement time point before Day 5 till Day 5 for AUCD5 Similarly, connecting the baseline or the first available viral load measurement time point before Day 28 till Day 28 for AUCD28
- Subjects with missing Day 5 measurements will have Day 5 viral load imputed from last and next available viral loads by linear interpolation for AUCD5 calculation. If viral load measurement is missing for Day 5 and all subsequent measurement days beyond Day 5, the subject will not have AUCD5 calculated and will be excluded from AUC analyses.
- Subjects with missing Day 28 measurements will not have AUCD28 calculated and will be excluded from AUC analyses.

Intermediate missing log 10-transformed viral loads (between baseline and the last day) will be linearly interpolated using the last and next available viral loads for AUC calculation for both AUCD5 and AUCD28. Subjects with intermediate missing values will be included in AUC analysis.

Time to viral load (as measured by DENV RNA and viral titre) or NS1 clearance, defined as time to first of 2 consecutive results of undetectable viral load or NS1, will be described using Kaplan-Meier methods. The median time to viral clearance and the estimated proportions of patients with viral clearance will be summarized by treatment group. Patients who do not receive a record of a negative test result by RT-PCR/viral titre or NS1 antigen assay by the last observation timepoint will be treated as censored at the final scheduled evaluation time point.

Subgroup analysis by DENV serotype will be carried out for the following endpoints: change of DENV viral load (as measured by DENV RNA and viral titre) from baseline, viral load AUC, time to viral load or NS1 clearance. Descriptive statistics (N, mean, standard deviation, median, minimum and maximum, and 95% CI) will be presented by treatment group.

Number and percentage of subjects with treatment-emergent amino acid substitutions in DENV NS5 gene will be compared between the treatment groups (chi-squared test).

Duration of fever is the sum of fever episode durations where fever episode duration is defined as the time from first fever measurement (either at baseline or following a period without fever) to the next measurement without fever. If the last episode has not resolved, duration for that episode will be

censored at the time of the last temperature measurement. Treatments will be compared by log-rank test.

Exploratory biomarkers may include plasma concentrations of cytokines (for example, TNF- $\alpha$ , IFN- $\gamma$ , IL-2, IL-4, IL-5, IL-6, IL-10, IL-12, IL-13, IL-1 $\beta$ , IP-10 and MCP-1). Data will be presented in descriptive statistics by treatment.

Exploratory analyses may be performed to evaluate exposure-response relationship. The relationship between the exposure of AT-752 (AT-281 and its metabolites AT-551, AT-229, and AT-273) and DENV viral load may be explored using graphical displays. Scatter plots of drug exposure versus change in DENC viral load will be provided.

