#### **Exploratory Endpoints: PD Endpoints**

- Change in DENV viral load (as measured by infectious viral titre) from baseline
- Area under the log10-transformed viral load curve (AUC) from first dose to the end of treatment or study (as measured by DENV RNA and viral titre)

- Time to viral load clearance, which is defined as the first of 2 consecutive undetectable viral load measurements [as measured by DENV RNA and viral titre]
- Time to clearance of NS1 protein using a NS1 antigen test. Clearance is defined as time from start of treatment until the first of 2 consecutive plasma samples are NS1-negative.
- Change of DENV viral load (as measured by DENV RNA and viral titre) from baseline, viral load AUC, time to viral load or NS1 clearance by DENV serotype
- Treatment-emergent amino acid substitutions in DENV NS5 polymerase
- Time to resolution or duration of fever
- Exploratory biomarkers on immunological response to dengue (See list in [Section 8.3.4](#))
- Exploratory analyses may be performed to evaluate exposure-response relationship. The relationship between the exposure of AT-752 (and its metabolites) and DENV viral load may be explored using graphical displays

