### **8.3.4 Pharmacodynamic Exploratory Analyses**

- Change in DENV viral load (as measured by viral titre) from baseline
- Area under the log10-transformed viral load curve (AUC) from first dose to the end of treatment (Day 5-6) and to study end (Day 28) (as measured by DENV RNA and viral titre)

- Time to viral load (as measured by DENV RNA and viral titre) or NS1 clearance, defined as time to first of 2 consecutive undetectable viral load or NS1, will be described using Kaplan-Meier methods. The median time to viral clearance and the estimated proportions of patients with viral clearance will be summarized by treatment group. Patients who do not receive a record a negative test result by RT-PCR/viral titre or NS1 antigen assay by the last observation timepoint will be treated as censored at the final scheduled evaluation time point.
- Change of DENV viral load (as measured by DENV RNA and viral titre) from baseline, viral load AUC, time to viral load or NS1 clearance by DENV serotype
- Treatment-emergent amino acid substitutions in DENV NS5 gene
- 
- Methods for analysis of time to resolution or duration of fever will be presented in the SAP
- Exploratory biomarkers may include plasma concentrations of cytokines (for example, TNF- $\alpha$ , IFN- $\gamma$ , IL-2, IL-4, IL-5, IL-6, IL-10, IL-12, IL-13, IL-1 $\beta$ , IP-10 and MCP-1)
- Exploratory analyses may be performed to evaluate exposure-response relationship. The relationship between the exposure of AT-752 (and its metabolites) and DENV viral load may be explored using graphical displays

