### 3.2.3 Exploratory Endpoints

Exploratory endpoints corresponding to exploratory objectives are:

Exploratory objective	Exploratory endpoints

PD	
 
• Change in DENV viral load (as measured by infectious viral titre) from baseline
 
• Area under the log 10-transformed viral load curve (AUC) from first dose to the end of treatment or study [as measured by DENV RNA and viral titre]
 
• Time to viral load clearance, which is defined as the first of 2 consecutive undetectable viral load measurements [as measured by DENV RNA and viral titre]
 
• Time to clearance of NS1 protein using a NS1 antigen test. Clearance is defined as time from start of treatment until the first of 2 consecutive plasma samples are NS1-negative.
 
• Subgroup analysis by DENV serotype: Change of DENV viral load [as measured by DENV RNA and viral titre] from baseline, viral load AUC, time to viral load, or NS1 clearance by DENV serotype
 
• Treatment-emergent amino acid substitutions in DENV NS5 polymerase
 
• Time to resolution or duration of fever
 
• Exploratory biomarkers on immunological response to dengue (See list in Section 12)
 
• Exploratory analysis to evaluate exposure-response relationship. The relationship between the exposure of AT-752 (and its metabolites) and DENV viral load measurement may be explored using graphic displays.
 

----	--

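### SAP section 12 defines the exploratory viral load AUC in two ways, stops the on-treatment version at Day 5 although dosing can run into Day 6, and adjusts neither version for baseline

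*SAP*

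**What the plan says.** **Quantity.** SAP section 12 opens its AUC text with "Area under the change of the log 10-transformed viral load curve (AUC) from first dose to the end of treatment (Day 5-6", and to Day 28. The following paragraph says that AUC_D5 and AUC_D28 "refer to area under the log 10-transformed viral load curve (AUC) from first dose to the end of treatment (Day 5" and Day 28 respectively. The derivation rule also uses the level: "AUC will be calculated from the log 10-transformed viral load curve connecting baseline or the first available viral load measurement time point before Day 5". SAP section 3.2.3 lists "Area under the log 10-transformed viral load curve (AUC) from first dose to the end of treatment or study". The protocol synopsis has "Area under the log10-transformed viral load curve (AUC) from first dose to the end of treatment or study", and protocol section 6.4 agrees. SAP section 14 declares no changes from the protocol.

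**Window.** Protocol section 8.3.4 takes the "viral load curve (AUC) from first dose to the end of treatment (Day 5-6) and to study end (Day 28". Within SAP section 12, Day 5-6 becomes Day 5 from one paragraph to the next.

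**Dosing and samples.** Protocol Tables 3-3, 3-4 and 3-6 place the last dose on Day 6 for mid-day and evening TID starts and for evening BID starts. All five sampling tables allow the Day 5 virology sample at any time that day. They place the end-of-treatment sample 8 to 24 hours after the last dose, on the Day 6 row.

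**Analysis.** The mixed models for RNA (SAP section 8.1.1) and titre (SAP section 12) include baseline viral load. The AUC is only to be presented by treatment, with no model, test or covariate named. The rule "A time-scaled trapezoidal rule will be used for AUC calculation" does not say what the scaling is.

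**The concern.** Two programmers could follow SAP section 12 correctly and produce different AUC tables, one with negative values and one with positive, and with different treatment differences. If this is not settled before unblinding, the choice can be made with results in view. Protocol section 5.4.1 and SAP section 13 both allow the sponsor unblinded reviews during the study.

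The window matters for a similar reason. A quantity labelled as running to the end of treatment should not stop before some subjects' last dose, and it should not pass over the one sample scheduled to mark that point.

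With about 15 subjects per group, baseline viraemia can differ noticeably by chance. Placebo is also pooled over three sequential cohorts, so a shift in baseline between cohorts could add to that. The plan handles this in its mixed models but not in the AUC.

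**Working it through.** The documents give no figure for the AUC, so there is none to reproduce. As a check on method, a noncentral t calculation at one-sided 0.10, SD 1.25 and effect 1 log10 gives power 0.810 for 15 vs 15 (stated 80%) and 0.592 for 15 vs 5 (stated 59%).

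**1. Level against change.** Write v0 for baseline log10 viral load and T for the length of the window. The trapezoid rule is linear, so

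- AUC(level) = AUC(change) + v0 × T
- divided by T: average level = average change + v0

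On nominal days T is 4 to Day 5, 5 to Day 6 and 27 to Day 28.

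Example (illustrative values): group A runs 8, 7, 6, 5, 4 on Days 1 to 5, and group B is the same curve 0.5 lower.

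| | A | B | A − B |
|---|---|---|---|
| AUC of level | 24.0 | 22.0 | 2.0 |
| AUC of change | −8.0 | −8.0 | 0 |

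If the curves stay parallel, the level difference is 0.5 × 5 = 2.5 to Day 6 and 0.5 × 27 = 13.5 to Day 28.

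**2. Chance imbalance at baseline.** The documents give no baseline SD, so a range is assumed. SE of the difference for 15 vs 15 = SD × √(2/15).

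| Assumed baseline SD | SE | P(gap over 0.5 log10) |
|---|---|---|
| 0.5 | 0.18 | 0.01 |
| 1 | 0.37 | 0.17 |
| 1.5 | 0.55 | 0.36 |
| 2 | 0.73 | 0.49 |

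**3. Unadjusted change is not free of baseline.** Once virus has reached a floor, level no longer depends on baseline, but change still does. Assume two subjects with baselines 8.0 and 7.5 who fall 1 log10 a day to a floor of 2 and are sampled on the protocol days. To Day 28:

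- Level AUC: 30 + 42 = 72.00 against 25 + 2.25 + 42 = 69.25, a difference of 2.75.
- Change AUC: 72 − 8 × 27 = −144.00 against 69.25 − 7.5 × 27 = −133.25, a difference of 10.75 in size.

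Here the change version carries more of the baseline gap, and it favours the subject with the higher baseline.

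**4. Effect of a baseline covariate.** With v0 as a linear covariate and a common T, the term v0 × T is absorbed into the coefficient of v0, so level and change give the same treatment difference. If each AUC is divided by the subject's own T, the two differ by exactly v0 and the result holds even when T varies.

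For precision, assume SD 1.05 for time-averaged change, baseline SD sb, baseline-change correlation r, and a true difference of 1 log10 (15 vs 15, one-sided 0.10):

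- SD(level) = √(sb² + 1.05² + 2 × r × sb × 1.05)
- SD(adjusted) = 1.05 × √(1 − r²)

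| sb | r | Change | Level | Adjusted |
|---|---|---|---|---|
| 2 | 0 | 90% | 47% | 90% |
| 1 | −0.4 | 90% | 87% | 94% |
| 1 | −0.5 | 90% | 91% | 95% |
| 1 | −0.7 | 90% | 98% | 99% |

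Unadjusted level beats unadjusted change once r < −sb/2.1, which is about −0.48 at sb = 1. The adjusted comparison was never below either one for r from 0 to −0.7.

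**5. Doses after Day 5, counted from the protocol's tables.**

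| Table | Start | Doses left after Day 5 |
|---|---|---|
| 3-2 | TID, before 10 AM | 0 of 15 |
| 3-3 | TID, 10 AM to 4 PM | 1 of 15 (7%) |
| 3-4 | TID, evening | 2 of 15 (13%) |
| 3-5 | BID, before 4 PM | 0 of 10 |
| 3-6 | BID, evening | 1 of 10 (10%) |

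With TID first doses allowed from 6 AM to 10 PM and the Day 5 sample at any hour, that sample falls between 3.1 and 4.75 days after Dose 1.

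**The case against.** The strongest reply is that the documents already show which quantity is meant. The level appears in the protocol's endpoint list and analysis section, in SAP section 3.2.3, in the named AUC_D5 and AUC_D28, and in the derivation rules. Change appears in one sentence, and SAP section 14 declares no departure from the protocol. This stands. It makes the change wording the outlier and decides which way to correct it, but the contradictory sentence still has to go.

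Second, the AUC is one of several exploratory endpoints, is only to be presented by treatment, and SAP section 4 calls all analysis descriptive. The RNA and titre models already adjust for baseline at every time point. This stands too and limits the weight of the point. A reader might take the AUC as the trial's main whole-course measure of antiviral effect, but neither document gives it that standing.

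Third, a reader might infer that the level definition costs a known amount of power, say from 90% down to 47-87%. Those figures can be computed, but only from an assumed SD of 1.05, an assumed baseline SD of 1 to 2, and a correlation no stronger than −0.4. Beyond about −0.48 at baseline SD 1 the ordering reverses. No AUC test is planned either; the one-sided 0.10 level belongs to the single-time-point power statement.

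Fourth, few doses fall after Day 5, and a fixed Day 5 window is a legitimate summary. That is right; the fault is in calling it the end of treatment.

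**Conclusion.** The point holds as an inconsistency to be corrected, with a useful gain in precision available at the same time. SAP section 12 gives two non-equivalent definitions of one endpoint, and they differ by baseline × T. The window called end of treatment closes before the last 1 or 2 of 15 TID doses, or the last of 10 BID doses, for late starters, and omits the end-of-treatment sample for all. Neither version is adjusted for baseline.

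Two stronger conclusions do not follow. Moving to unadjusted area under the change would not remove baseline dependence, and to Day 28 it can increase it. Nor is the level version biased by design: within a randomised cohort a baseline gap is chance, and only cohort-to-cohort shifts in the pooled placebo group could add a systematic part. How much precision the covariate gains depends on the baseline SD and the baseline-change correlation, which the documents do not give. The primary analysis is not affected.

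**What to change.** In SAP section 12:

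1. Keep the protocol's area under the log10 viral load level and strike the reference to change from the opening AUC sentence. If change is really intended, record it in section 14 as a departure from the protocol.
2. Compare arms with baseline viral load as a covariate, for both the on-treatment and the Day 28 windows.
3. Define the time scaling, for example AUC divided by the subject's actual interval from first dose to last included sample.
4. End the on-treatment AUC at the sample taken 8 to 24 hours after the last dose, or keep Day 5 and drop the end-of-treatment label. Adapt the missing-Day-5 interpolation rule to whichever is chosen.

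The cost is a few lines of SAP text and a small programming change before unblinding. The baseline and end-of-treatment samples are already collected. The one trade-off is in item 4: the end-of-treatment sample gives windows of unequal length, which the time-averaging in item 3 puts on a common scale.
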